3.4 CRITERIA FOR ADDITIONAL CYCLES

Patients will be eligible to continue to receive mithramycin for as long as they do not experience clinical or radiographic disease progression and tolerate mithramycin (defined as not meeting off treatment criteria). If a patient experiences DLT on a reduced dose of mithramycin (as defined in Section 3.3), no further mithramycin will be administered.

Patients may receive the next cycle at the same dose level (or reduced level as above) if:

- 1) patient has stable or responding disease;
- 2) has a platelet count \geq 75,000/mcL, and an ANC \geq 1000/mcL, and meets other laboratory parameters defined in the eligibility section; and
- 3) has not met any criteria for removal from treatment or off study (Section 3.7)

3.5 On Study Protocol Evaluation ([APPENDIX 3: STUDY CALENDAR](#))

3.5.1 Monitoring During Active Treatment:

3.5.1.1 History and physical exam: at baseline and weekly.

3.5.1.2 Weight: at baseline and recommended daily days 2 to 7 each cycle

3.5.1.3 A 12-lead EKG will be performed day 1 and 7 of each cycle, and day 4 of cycle 1. All EKGs should be done prior to drug infusion on that day and as close as possible to the time the trough PK is drawn. Document the time the EKG is performed on the PK sheet ([Appendix 4: Pharmacokinetic Worksheet for Mithramycin \(Phase I and Phase II For nursing staff\)](#))

3.5.1.4 Laboratory evaluation:

CBC with differential count daily (starting on day 2 to day 7) during mithramycin administration; then twice weekly during cycles 1-3. During subsequent cycles: CBC with differential count twice weekly during administration, then weekly.

Chemistry: sodium, potassium, chloride, CO₂, creatinine, glucose, BUN, albumin, calcium, magnesium, daily (starting on from day 2 to day 7) during drug administration; then twice weekly during cycles 1-3. During subsequent cycles chemistries are performed weekly.

Liver Function Tests: alkaline phosphatase, ALT/GPT, AST/GOT, total bilirubin, total protein, daily (starting on day 2 to day 7) during drug administration; then twice weekly during cycles 1-3. During subsequent cycles chemistries are performed weekly.

Coagulation Studies: PT/PTT/Thrombin Time, Fibrinogen prior to and once on days 3, 4 or 5 and days 7, 8, or 9 of every cycle. In addition, prior to cycle 1 and 2, 1 mL of plasma will be obtained, filtered through a 0.22 micron filter, frozen and saved for future clinical reference if needed (See [Appendix 8: Plasma samples for clinical purpose](#)).

Pregnancy test for women of child-bearing age: prior to each cycle.

Urinalysis: prior to each cycle.

3.5.1.5 Tumor Measurements:

Disease evaluations will be performed after every EVEN numbered treatment cycle, i.e. cycle 2, cycle 4, etc, and when removed from treatment, when feasible: Assessment of disease sites will be performed using the most appropriate radiological evaluation. This could include a CT scan of chest, abdomen and pelvis and primary tumor, bone scan, FDG-PET or MRI as indicated. A consistent method of disease evaluation will be used throughout the study. Imaging studies used for response evaluation will be sent to the NCI POB for volumetric analysis as secondary endpoint (See **Appendix 9: Imaging studies for volumetric analysis of tumor burden**).

3.5.2 Monitoring after completion of treatment with mithramycin:

After completion of therapy, patients will be monitored until recovered from toxicity to baseline or stabilized.

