1.2.2.1 Preclinical toxicology

In mice, the LD₅₀ was determined to be about 2000 mcg/kg (6000 mcg/m²) of body weight. This dose is higher than the 100 mcg/kg of body weight that was found to be lethal in some dogs (2000 mcg/m²) and monkeys (1200 mcg/m²) (25). However, the drug was found to be essentially non-toxic in dogs and monkeys administered at a dose of 24-50 mcg/kg/day (480-1000 mcg/m² dog, 288-600 mcg/m² monkey) intravenously for 24 consecutive days (25). The most frequently encountered toxicities at higher doses were bleeding, anorexia, vomiting, elevated liver function tests, electrolyte abnormalities, bone marrow suppression and azotemia (25).

In our experience in mice, doses of 1 mg/kg/day three times a week for 6 weeks delivered via intraperitoneal injection was essentially non-toxic to the mice. At necropsy, the mice treated at this dose and schedule had mild hypoalbuminemia, slightly increased ALT/AST with some evidence of liver toxicity described as mild to moderate and minimal thrombocytopenia.

It is notable that we were able to show that the drug interferes with the expression of the EWS-FLI1 downstream target NR0B1 in our mouse models at this 1 mg/kg/day dose. However, it is not clear if the dose of 25 mcg/kg/dose is high enough to interfere with EWS-FLI1 activity in patients. Therefore, one of the primary objectives will be to establish the inhibition of NR0B1 expression through mandatory tumor biopsies when feasible (see Section **Error! Reference source not found.**). These results will be critical for the interpretation of patient response to treatment, as

well as the future clinical development of mithramycin and the preclinical development of mithramycin analogs.

Administration of tritium labeled mithramycin to monkeys showed a terminal half-life of 5 hours. The peak cerebrospinal fluid concentration: plasma ratio was 0.12 and reached after 1 ½ hours (26). Preliminary pharmacokinetic parameters of ¹²⁵I-plicamycin (mithramycin) in human plasma using a radioimmunoassay were described (27). Three patients were studied and received mithramycin at a dose ranging from 0.85 to 1.0 mg/m² IV over 2 hours. Drug elimination was biphasic, with a mean elimination half-life of 10.6 hours (±1.7), and a clearance rate of 11.1± 0.4 ml/min/m².

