2.2.4 Cardiac Function Studies

Assessment of cardiac function (ejection fraction/shortening fraction) must be performed within 4 weeks of enrollment by MUGA or Echocardiogram to rule out cardiomyopathy. In addition, a 12-lead EKG must be performed.

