3.5.3 Off Study Evaluation (at least 30 days after last dose)

3.5.3.1 History and physical exam

3.5.3.2 12-lead EKG

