4.6 QTc PROLONGATION

If grade 3 or 4 QTc prolongation is noted on a 12-lead EKG, then repeat the 12-lead EKG to confirm finding and consult cardiology. Hold next dose until cardiology consult is obtained.

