^pFor patients who have discontinued mithramycin infusions during any cycle prior to completion of the 7 daily infusions, the required laboratory studies and other evaluations can be adjusted by the principal investigator or associate investigator as necessary.

11.4 APPENDIX 4: PHARMACOKINETIC WORKSHEET FOR MITHRAMYCIN (PHASE I AND PHASE II) FOR NURSING STAFF

DAY 1

Patient ID		Weight (kg), height (cm), BSA (m ²)	
Dose level (mg/kg)		Total dose (mg)	
Date:		Infusion start time	
		Infusion stop time	
Pre-dose EKG time:		Signature of person completing EKG:	

Sample #	Hour	Target Time	Actual Time	Signature
1	pre dose			
2	3 h post-start of infusion			
3	Just prior to the end of the 6 hour infusion			
4	0.25 h post-infusion			
5	0.5			
6	1			
7	2			
8	3			
9	5			
10	7			
11*	9-12			

*If feasible

Abbreviated Title: Ph I/II Pediatric Mithramycin**Version Date:** 11/09/2016

Collect 3 mL blood in a lavender top tube. Blood has to be drawn from a site away from the site of infusion (cannot be drawn through the line used to infuse drug, or through another lumen of that line).

Following blood collection, the tubes should be inverted several times to ensure mixing with the anticoagulant. Tubes should then be placed on crushed ice, and samples should be centrifuged for 15 minutes at approximately 1000 x g at 0-5 °C within 2 hr after collection. The plasma should be transferred to separate pre-labeled screw-capped polypropylene transfer tubes and stored at -80°C until shipped to the analytical site.

Patient ID		Weight (kg), height (cm), BSA (m ²)	
Dose level (mg/kg)		Total dose (mg)	

Day 2 Date: _____ Infusion start time: _____ Stop time: _____

Sample #	Hours	Target Time	Actual Time	Signature
1	pre dose			
2	End of infusion			

Day 4 Date: _____ Infusion start time: _____ Stop time: _____

Pre-dose EKG Time: _____ Signature of person completing EKG: _____

Sample #	Hours	Target Time	Actual Time	Signature
1	pre dose			
2	End of infusion			

Day 7 Date: _____ Infusion start time: _____ Stop time: _____

Pre-dose EKG Time: _____ Signature of person completing EKG: _____

Sample #	Hours	Target Time	Actual Time	Signature
1	pre dose			
2	End of infusion			

Day 8* Date:

Sample #	Hours	Target Time	Actual Time	Signature
1	24 hours after day 7 dose			

2	24.5 hours after day 7 dose			
---	--------------------------------	--	--	--

Day 9* Date:

Sample #	Hours	Target Time	Actual Time	Signature
*1	48 hours after day 7 dose			
*2	48.5 hours after day 7 dose			

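### No scheduled EKG falls near the end of an infusion, so QTc effects near peak mithramycin concentration are not assessed

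*Combined protocol and SAP*

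**What the plan says.** Section 3.5.1.3 sets the on-treatment schedule: "A 12-lead EKG will be performed day 1 and 7 of each cycle, and day 4 of cycle 1". It fixes the timing in the next sentence: "All EKGs should be done prior to drug infusion on that day and as close as possible to the time the trough PK" is drawn. Note n of the Study Calendar (Appendix 3) gives the same pre-infusion rule and limits the day 4 EKG to cycle 1. The nursing PK worksheet (Appendix 4) has a field labelled "Pre-dose EKG time" for each EKG day and no field for an EKG at any other time.

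The other scheduled EKGs are taken off drug. Section 2.2.4 covers screening ("In addition, a 12-lead EKG must be performed"), and Section 3.5.3 asks for one at the off-study visit, at least 30 days after the last dose.

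Two rules use these readings. Section 4.6 begins "If grade 3 or 4 QTc prolongation is noted on a 12-lead EKG" and then calls for a repeat EKG, a cardiology consult and a hold on the next dose until the consult. Section 3.1.1 counts any non-hematologic toxicity of grade 3 or higher that is at least possibly related as a DLT, apart from five listed exceptions; QTc prolongation is not among them.

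Section 5.1 and Appendix 4 already place PK samples at the end of the infusion on days 1, 2, 4 and 7 of cycle 1. QTc is not named as an objective or endpoint, and Section 8 contains no QTc analysis.

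**The concern.** Determining toxicity is a primary objective of the phase I portion (Section 1.1.1.1), and cycle 1 DLTs decide escalation and the MTD (Section 3.1.2). If mithramycin prolongs QTc in step with its concentration, the effect is largest around the end of each infusion, and no EKG is scheduled then. A grade 3 event confined to those hours would trigger neither Section 4.6 nor the DLT count unless an unscheduled EKG happened to catch it.

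The historical record does not fill the gap. Section 1.2.3 says that earlier toxicities were not studied systematically, and the only cardiotoxicity report it found gives no details. Section 1.2.5 reports no formal pediatric study.

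**Working it through.** The documents give no figure for QTc detection, so there is none to reproduce. The check has two parts: count the EKGs by time relative to the infusion, then estimate how far the level has fallen when they are taken.

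**Count.** Cycle 1 has three on-treatment EKGs (days 1, 4, 7), and each later cycle has two (days 1, 7). None is near the end of an infusion. The cycle 1 day 1 EKG is drug-free, and later day 1 EKGs follow about three weeks without drug (28-day cycle, last dose on day 7). EKGs with drug on board are therefore days 4 and 7 of cycle 1 and day 7 of later cycles.

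**Inputs.**
- Infusion of 6 h once daily for 7 days (Section 3.1), so a pre-dose reading falls 24 − 6 = 18 h after the previous infusion ended.
- Human half-life from Section 1.2.2.1: "Drug elimination was biphasic, with a mean elimination half-life of 10.6 hours" (±1.7), from three patients given 2-hour infusions. The range is 8.9 to 12.3 h.

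**One-compartment decline.** With k = ln 2 / half-life, the pre-dose level as a share of the previous end-of-infusion level is exp(−18k). At 10.6 h, k = 0.0654 per hour and exp(−18 × 0.0654) = 0.308. Relative to the same day's end of infusion, superposition of doses gives exp(−18k) × (1 − exp(−72k)) / (1 − exp(−96k)) on day 4. On day 7 the exponents 72 and 96 become 144 and 168.

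| Half-life (h) | exp(−18k) | Day 4 share | Day 7 share |
|---|---|---|---|
| 8.9 | 0.246 | 0.245 | 0.246 |
| 10.6 | 0.308 | 0.306 | 0.308 |
| 12.3 | 0.363 | 0.358 | 0.363 |

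The end-of-infusion level is thus about 1/0.363 = 2.8 to 1/0.246 = 4.1 times the pre-dose level. With the 5 h monkey half-life from the same section, the share would be 0.082.

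**Biphasic elimination.** Section 1.2.2.1 gives no early half-life, so this step is an assumption: early half-life 0.5 to 2 h, early-to-late amplitude ratio 1 to 9, late half-life 10.6 h. For a 6-hour infusion, each phase with rate constant a contributes amplitude × (1 − exp(−6a)) / a per dose at the end of infusion. For the late phase with accumulation this is (0.325 / 0.0654) / 0.792 = 6.27.
- Half-life 0.5 h, ratio 1: early contribution 0.72; share = 0.308 × 6.27 / (6.27 + 0.72) = 0.28.
- Half-life 2 h, ratio 9: early contribution 9 × 2.52 = 22.7, of which 0.04 remains at 18 h; share = (1.93 + 0.04) / (6.27 + 22.7) = 0.07.

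The one-compartment share is therefore more likely too high than too low.

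**Day 4 against day 7.** The ratio of the two pre-dose levels is 1 / (1 + exp(−72k)), which is 0.98 to 1.00 over the half-life range. On this model the two pre-dose EKGs observe almost the same exposure.

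**The case against.** The strongest reply has four parts.

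First, a reader might infer that the trial cannot detect concentration-related QTc prolongation at all. The documents do not support that. The day 4 and day 7 EKGs are taken with drug on board, have drug-free comparators (screening and cycle 1 day 1), and in cycle 1 sit beside a trough PK sample. A large, delayed or persistent effect could appear. The repeat EKG in Section 4.6 also has no stated timing. This part of the reply stands and limits the point to effects near peak.

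Second, QTc is not a planned endpoint, and the documents report no QTc signal: the toxicity list in Section 10.1.2 has no such item. This also stands. The documents give no effect size in milliseconds, so none is claimed here. But the protocol itself acts on QTc in Section 4.6 and leaves it inside the DLT definition, so the timing of the reading matters to its own rules.

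Third, pre-dose timing has a use: a reading before the infusion can inform that day's dose. This stands and decides which EKG to move. Re-timing day 7 in every cycle would remove the only on-drug pre-dose EKG from cycle 2 onward, where no paired PK sample is scheduled.

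Fourth, Section 4.2 allows ondansetron or similar antiemetics before and after mithramycin. The documents say nothing about their effect on QTc, but a reading near the end of infusion could be harder to attribute to mithramycin. This is a reason to record antiemetics with the reading, not to omit it.

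**Conclusion.** The point holds in a limited form. Section 3.5.1.3, Appendix 3 note n and the Appendix 4 worksheet agree that every on-treatment EKG is pre-dose, when the level is about 31% of the end-of-infusion level (25% to 36% over the stated half-life range, possibly lower). QTc effects near peak concentration are not assessed, and Section 4.6 and the cycle 1 DLT count draw on pre-dose readings only, apart from any unscheduled EKG.

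The ratio is indicative: it rests on three patients, a shorter infusion and one-compartment decline. Reading it as the share of a QTc effect further assumes that the effect is proportional to concentration without delay. A reader might go on to infer that the drug has a QTc hazard being missed, but nothing in the documents shows one. The gap is in what the schedule can observe, and it is cheap to narrow.

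**What to change.** Re-time one existing cycle 1 EKG, preferably day 4, to just before the end of the infusion, next to the end-of-infusion PK sample already drawn that day. Keep the day 1 and day 7 pre-dose EKGs in all cycles. Leave later cycles and the Section 4.6 action rule as they are. Cycle 1 then has a drug-free baseline, a near-peak reading and an on-drug trough, each with a paired PK sample.

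Text to amend: Section 3.5.1.3, Appendix 3 note n, and the day 4 EKG line in Appendix 4. Add to Section 8.5 a descriptive summary of cycle 1 QTc change from the day 1 baseline against the paired concentration, with concomitant antiemetics such as ondansetron noted.

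Cost: four wording changes, with no added EKG, visit or blood draw. The cycle 1 day 4 pre-dose EKG is lost, so that reading can inform the day 5 dose but not the day 4 dose. The exposure it would have observed is nearly the same as at the day 7 pre-dose EKG, which stays. In adults having the on-treatment biopsy (day 4 ± 1 day, Appendix 7), the EKG and biopsy times would need to be coordinated.

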3.5.2.1 History and physical exam weekly

3.5.2.2 Laboratory evaluation: CBC, Acute, Hepatic and Mineral panels, uric acid, LDH, PT/PTT weekly

3.5.3 Off Study Evaluation (at least 30 days after last dose)

3.5.3.1 History and physical exam

3.5.3.2 12-lead EKG

3.5.3.3 Laboratory evaluation: CBC, Acute, Hepatic and Mineral panels, uric acid, LDH, PT/PTT

The patient may have evaluations and lab work obtained through his or her local physician between cycles or during follow up.

3.6 CONCURRENT THERAPIES

Other cancer chemotherapy, radiation, immunotherapy, biologic therapy, or investigational agents cannot be administered to patient while receiving mithramycin.

3.7 CRITERIA FOR REMOVAL FROM PROTOCOL THERAPY AND OFF STUDY CRITERIA

3.7.1 Criteria for removal from protocol therapy

1. A patient may be removed from the protocol for the following non-medical or administrative reasons:
 - a. Patient refusal of further treatments (reasons must be noted on the patient's CRF).
 - b. It is deemed in the best interest of the patient. In this instance the PI should be notified and the reasons of withdrawal should be noted in the CRF.
 - c. Serious protocol violation as determined by the PI.
2. Any patient who develops DLT and does not recover from the toxicity by day 42 after the start of the cycle (Section **3.1.1** and Section **3.4**)
3. Any patient who develops any one of the following:
 - a. grade 3 or 4 anaphylaxis or allergic reaction;
 - b. grade 4 DIC;

- c. grade 4 erythema multiforme, toxic epidermal necrosis (TEN), or Stevens-Johnson syndrome);
- d. grade 4 diarrhea;
- e. grade 3 hemorrhage if endoscopic or operative intervention required or any grade 4 hemorrhage;
- f. grade 2 or greater bleeding that does not resolve within 6 hours of administration of appropriate treatment;
- g. CNS hemorrhage of any grade.
- 4. Any patient who does not recover from the toxicity by day 42 to meet criteria to start additional cycles (Section 3.4).
- 5. Any patient who develops DLT after a dose reduction for DLT (Section 3.3) unless the patient continues to receive benefit from mithramycin. Patients who received initial treatment at 25mcg/kg will be allowed two dose reductions prior to coming off treatment.
- 6. Any patient with clinical or radiographic evidence of progressive disease on treatment, as defined in Section 6.2, following any treatment cycle will be removed from the treatment.
- 7. A patient who develops a concurrent serious medical condition that might preclude or contraindicate the further administration of mithramycin will be removed from treatment.
- 8. A patient who becomes pregnant will be immediately taken off therapy.
- 9. Patients who are taken off protocol therapy due to toxicity are to be followed, if feasible, until toxicity resolves to baseline or grade 1 or less. Follow-up data will be collected until off study criteria are met unless consent is withdrawn.

3.7.2 Criteria for removal from Study

- 1. Death
- 2. Lost to follow-up
- 3. Withdrawal of consent for any further data submission
- 4. Entry onto another therapeutic study
- 5. Patients who are taken off treatment for toxicity will be followed until resolution of toxicity and then taken off study (at least 30 days after the last dose of mithramycin).
- 6. The PI deems it is in the best interest of the patient

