6.2.2 Confirmatory Measurement/Duration of Response

a. Confirmation

To be assigned a status of PR or CR, changes in tumor measurements must be confirmed by repeat assessments that should be performed at least 4 weeks after the criteria for response are first met. Objective response measures will be confirmed at the Coordinating Center. The participating site should forward staging studies of participants who have achieved PR or CR status to the Coordinating Center for confirmation.

b. Duration of Overall Response

The duration of overall response is measured from the time measurement criteria are met for CR or PR (whichever is first recorded) until the first date that recurrent or

progressive disease is objectively documented (taking as reference for progressive disease the smallest measurements recorded since the treatment started).

The duration of overall CR is measured from the time measurement criteria are first met for CR until the first date that progressive disease is objectively documented.

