8.2.1 Methods of Analysis

Patients who are considered evaluable for response will be included in an analysis of time to progression. Time to progression will be estimated using the product-limit method of Kaplan and Meier. The probability of progression free survival at 6 months will be summarized. Response rates will be calculated as the percent of patients whose best response is a CR or PR, and the fraction of responses obtained will have a 95% confidence interval, which takes into consideration the two-stage nature of the design (50). Toxicity information recorded will include the type,

severity, time of onset, time of resolution, and the probable association with the study regimen. Tables will be constructed to summarize the observed incidence by severity and type of toxicity.

Time to progression will be taken as the number of days from enrollment until: (1) disease progression; (2) death because of treatment complications; (3) resection of measurable tumor; or (4) last patient follow-up whichever is first. Patients will be considered to have experienced a progression event if (1) or (2) occurs. Otherwise, the patient will be considered censored for time to progression.

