^c1 mL of plasma will be obtained, filtered through a 0.22 micron filter, frozen and saved by hematology pathology for future reference if needed, prior to receiving drug on day 1 of cycle 1 and 2 only. See **Error! Reference source not found.** for details.

^dCoagulation studies: drawn on days 1, (3, 4 or 5) and (7, 8 or 9) or as clinically indicated. If screening coagulation studies drawn within 1 week of starting drug, day 1 can be omitted for cycle 1 only.

^eExcluded by history only. No laboratory testing of HIV, HBV or HCV is required.

^frequired at screening/prior to cycle 1 and prior to each subsequent cycle on females of childbearing potential

^grequired at screening/prior to cycle 1 and prior to each subsequent cycle

^gperformed after every EVEN numbered treatment cycle, i.e. cycle 2, cycle 4, etc until off therapy and then every two months until off study or as indicated by clinical response criteria see (section 6.2). Imaging studies will be sent to NCI POB for volumetric analysis (see **Error! Reference source not found.** for details).

^hPK samples: prior to and at the completion of the first infusion, then trough and end of infusion samples with day 4 and 7 doses, and 24 and 48 hours after day 7 dose. Samples will therefore be drawn on days 1, 2, 4, 7, 8, 9 as indicated in **Error! Reference source not found.** and **Error! Reference source not found..**

ⁱA serum sample for potential biomarker analysis will be obtained prior to the first mithramycin injection, and then at the time of each restaging studies. See **Error! Reference source not found.** for details.

^jEligibility and timing for mandatory biopsy is defined in **Error! Reference source not found..**

^kSee **Error! Reference source not found.** to obtain sheet to record adverse events at home

^lSee **Error! Reference source not found.** to record all medications taken at home

^mPost therapy evaluations will be completed until at least 30 days after the last dose of mithramycin and until resolution of toxicity.

ⁿAll EKGs should be done prior to infusion. EKG on day 4 to be done on cycle 1 only.

^o2.5 mg dexamethasone/m² BSA PO or IV starting 12 hours before the first dose of mithramycin, then prior to the first dose, and then twice daily for 24 hours after the last dose of mithramycin

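### Patients stopped for toxicity leave the study once toxicity resolves, so a response can go unconfirmed and time to progression is censored by a treatment outcome

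*Combined protocol and SAP*

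**What the plan says.** Section 3.7.2 lists six ways to leave the study. Item 5 is the only one that depends on why treatment stopped: "Patients who are taken off treatment for toxicity will be followed until resolution of toxicity and then taken off study", with the limit "at least 30 days after the last dose of mithramycin". It mentions neither progression nor imaging.

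Other provisions determine what that exit means:

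- Section 3.7.1 item 9 ends data collection at the same point: "Follow-up data will be collected until off study criteria are met unless consent is withdrawn".
- Section 3.5.1.5 sets the restaging schedule: "Disease evaluations will be performed after every EVEN numbered treatment cycle". It also asks for an evaluation at removal from treatment where that is feasible.
- Appendix 3, footnote g on imaging, schedules scans after therapy: "then every two months until off study or as indicated by clinical response criteria", with a pointer to section 6.2.
- Section 6.2.2 requires a PR or CR to be confirmed by "repeat assessments that should be performed at least 4 weeks after the criteria for response are first met".
- Section 8.3 counts only confirmed responses and treats all other evaluable patients as non-responders.
- Section 8.2.1 ends the time-to-progression (TTP) clock at progression, death from treatment complications, resection or "last patient follow-up whichever is first". Only the first two are events; otherwise the patient is censored.

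**The concern.** Two endpoints depend on disease assessment continuing after treatment stops, and item 5 can end it early for one group.

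The first is the primary endpoint. A patient observed on therapy for at least one cycle is evaluable under section 8.3 and stays among the 24. If that patient's response is seen once and the patient then leaves under item 5, the response cannot be confirmed and counts against the drug. In a design that stops at 0 of 9 and declares activity at 3 of 24, one such patient can change the decision.

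The second is TTP. A patient without progression who leaves under item 5 is censored at a time set by toxicity and its resolution. Kaplan-Meier estimation assumes that censored patients carry the same later risk as those still followed. Patients who have come off the drug for toxicity may not, and the plan offers no reason to expect that they do.

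**Working it through.** **1. The plan's own design figures.** Inputs from section 8.2: p0 = 0.05, p1 = 0.25, n1 = 9 (stop at 0 responses), N = 24 (success at 3 or more), so n2 = 15.

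P(success) = 1 − P(X1=0) − P(X1=1)·P(X2≤1) − P(X1=2)·P(X2=0)

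- At p0: P(X1=0) = 0.95^9 = 0.630, the stated 63% chance of early termination. Alpha = 0.093, within the 0.10 limit.
- At p1: 1 − 0.0751 − 0.2253×0.0802 − 0.3003×0.0134 = 0.903, against the stated 0.90.

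The design reproduces. The issue is ascertainment, not the sample size.

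**2. Calendar.** Inputs: seven daily doses every 28 days (section 3.1), so the last dose of a full cycle k falls on day 28(k−1)+7; 30-day minimum (3.7.2 item 5); scans after even cycles, about days 56 and 112 (3.5.1.5); confirmation at least 28 days after first response (6.2.2). The off-study days assume that toxicity has resolved by the 30-day minimum.

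| Last dose in | Last-dose day | Earliest off study | Relevant assessment |
|---|---|---|---|
| Cycle 1 | 1–7 | 31–37 | First restaging about day 56 |
| Cycle 2 | 29–35 | 59–65 | Response at 56, confirmable from 56+28 = 84 |
| Cycle 3 | 57–63 | 87–93 | Confirmable from 84; next scheduled scan about 112 |
| Cycle 4 | 85–91 | 115–121 | Response at 112, confirmable from 112+28 = 140 |

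After a full cycle 2 the shortfall is 84 − 65 = 19 days; after a full cycle 4 it is 140 − 121 = 19 days. After cycle 3, confirmation is possible in time, but only with a scan ahead of schedule.

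**3. What lost responses would cost.** Let q be the share of true responders who leave before confirmation. The documents give no value for q, so this is a range of assumptions. The effective response rate is 0.25(1−q), put through the formula in step 1.

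| q | Effective rate | Power | Chance of stopping at stage 1 |
|---|---|---|---|
| 0 | 0.250 | 0.903 | 7.5% |
| 5% | 0.2375 | 0.884 | 8.7% |
| 10% | 0.225 | 0.862 | 10.1% |
| 20% | 0.200 | 0.805 | 13.4% |
| 30% | 0.175 | 0.728 | 17.7% |

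**4. TTP illustration.** Assumptions: exponential TTP with a median of 120 days in patients not stopped for toxicity; 20% stopped for toxicity and censored at day 37 or day 65; their progression hazard set at a multiple of the others' hazard. Simulated progression-free proportion at day 182:

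| Hazard multiple | True | Kaplan-Meier |
|---|---|---|
| 2 | 0.305 | 0.332 |
| 1 | 0.350 | 0.350 |
| 0.5 | 0.399 | 0.362 |

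The estimate is too high, unbiased or too low according to a hazard that the documents do not supply.

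**The case against.** The strongest reply is that the gap is narrow and partly covered already. Much of this stands.

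- **19 days is a worst case.** Thirty days is a minimum; the trigger is resolution of toxicity. Items 2 and 4 of section 3.7.1 apply only when toxicity has not recovered by day 42 of the cycle, which in cycle 2 is study day 28 + 42 = 70. Those patients leave later still, so their shortfall is under 84 − 70 = 14 days and may be nil. Day 65 fits mainly the immediate-stop events of item 3, or item 5 of that section. The ±7-day window in section 7.2.4 also makes exact days too precise.
- **Some scans are provided for.** Footnote g allows imaging as the response criteria require and points to section 6.2, which holds the confirmation rule. If a removal scan on day 35 already shows the response, confirmation is possible from 35 + 28 = day 63, before day 65. But nothing says that item 5 waits for the confirming scan, and the removal scan is required only where feasible.
- **Some responders would not be stopped.** Section 3.7.1 item 5 exempts patients still benefiting from removal after a repeat DLT. Section 3.4 reads differently, and the two need reconciling in their own right.
- **The contrast with other patients is blurred.** A reader might infer two clean follow-up tracks. Section 3.5.2 and footnote m describe post-therapy monitoring in toxicity-based terms whatever the reason for stopping. Neither takes other patients off study, but the texts do not establish a sharp division.
- **TTP carries little decision weight.** It is secondary, to be defined preliminarily, with no test. With 24 patients and a 6-month figure near 30%, the 95% half-width is about 1.96·√(0.3×0.7/24) = 0.18, well above the shifts of 0.03 to 0.04 in the illustration.

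What remains is a written rule that, followed as it stands, can end assessment before confirmation.

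**Conclusion.** The point holds as a gap in follow-up that can lose confirmed responses. The calendar follows from the plan's own schedule, given toxicity that resolves by the 30-day minimum and no earlier scan showing the response. The effect on power rests entirely on an assumed q: at 10%, power falls from 0.903 to about 0.86. The documents say nothing about how many responders would be affected.

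Two stronger readings are not supported. One is that responses in patients stopped for toxicity are routinely lost, or always miss confirmation by 19 days. That is the worst case only. The other is that the 6-month figure will be too high because it favours patients who tolerated the drug. The direction depends on the off-drug hazard, and a lower hazard reverses it. What can be said is that censoring depends on a treatment outcome, so its independence cannot be assumed.

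The change is worth making because it protects the primary endpoint at little cost.

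**What to change.** Amend section 3.7.2 item 5 in two respects:

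1. Patients stopped for toxicity without progression stay on study for disease assessment, on the two-monthly imaging of footnote g, until progression, new anticancer therapy or withdrawal.
2. Any PR or CR not yet confirmed has its confirming scan, at least 4 weeks after the response was first seen, before the patient goes off study.

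Reconcile item 5 with section 3.5.2 and with footnotes g and m of Appendix 3, so that they agree on when disease assessment ends for each group.

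A sensitivity analysis that counts removal for toxicity as a TTP event is not needed. It would turn the endpoint into something closer to time to treatment failure, and it adds little once follow-up runs to progression.

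The cost is a wording change and a few more follow-up scans on a schedule the protocol already contains. No dosing or treatment rule changes.
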